This is a prospective observational study of patients undergoing vaginal treatment with the fCO₂ laser for various urogenital symptoms. We anticipate enrolling approximately 100 women in this study. The majority of patients are expected to be recruited from the WUC and private Urology offices. Informed consent will be obtained before any study activities are conducted. Women who meet all of the eligibility criteria will be enrolled in the study. Three treatments with the fCO₂ laser to the vagina will be performed, approximately six weeks apart. The patient will follow up every three months for the first year, then every six months for the following two years, for a total of three years of follow-up.

At each follow-up visit, the patients will complete specified questionnaires. The patient will be offered a repeat treatment at 1, 2 and 3 years if initial treatment efficacy has decreased. A pelvic examination will be performed at Visits 4 (6-month follow up), 6 (12-month follow up), 8 (24-month follow up), and 10 (36-month follow up) and the clinician will complete a cough stress test and the VHIS, including vaginal pH.

Patients will be advised to refrain from:

- vaginal intercourse for 24 hours prior to all visits.
- starting vaginal or systemic hormone therapy or use of new vaginal lubricants during the first six months of the study.
- starting any other preventative therapies for UTIs including antibiotic suppression, cranberry supplements, or d-mannose during the first six months of the study.
- starting any new treatments (i.e. pharmacologic, physical therapy) for overactive bladder (OAB) or stress urinary incontinence (SUI) during the first six months of the study.

Study patients will not be compensated for their participation in the trial. However, all research related activities, specified on the table of events, will be provided at no cost to the study patient.

Inclusion/Exclusion Criteria

Inclusion criteria:

- Female
- ≥18 years and ≤90 years of age
- One or more of the following indications for fCO₂ laser treatment:
 - Genitourinary symptoms of menopause, including after natural, medically-induced, or surgical menopause
 - Vaginal dryness, burning, itching, or dyspareunia not related to menopause
 - Recurrent UTIs, defined as 4 or more in a year
 - Overactive bladder
- Must sign the informed consent form
- Must be willing to comply with the study protocol

Exclusion criteria:

- Contraindications to fCO₂ laser treatment, such as:

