Visit 2 – Treatment 2 (6 weeks +/- 2 weeks after Visit 1)

Current medications and AEs will be assessed. Urine dipstick, and urine culture will be performed, if indicated. UTI symptoms will be assessed. Urine pregnancy test will be done in women of childbearing capability. The patient will complete a PGI-I for symptom improvement, VSQ, I-QOL, QUID, OAB-q SF, FSFI, GAD-7 and PHQ-8. A vaginal exam, including a cough stress test and VHIS, will be performed. A vaginal swab will be collected for wet mount and examined microscopically for presence of lactobacillus. The fCO₂ laser treatment will be performed, and patient will score discomfort using the VAS. The provider will score the difficulty of administering the treatment using the VAS. The patient will complete a three-day voiding diary within 1 week prior to Visit 3, which will be collected at Visit 3.

Visit 3 – Treatment 3 (6 weeks +/- 2 weeks after Visit 2)

Current medications and AEs will be assessed. Urine dipstick, and urine culture will be performed, if indicated. UTI symptoms will be assessed. Urine pregnancy test will be done in women of childbearing capability. The patient will complete a PGI-I for symptom improvement, VSQ, I-QOL, QUID, OAB-q SF, FSFI, GAD-7 and PHQ-8. A vaginal exam, including a cough stress test and VHIS, will be performed. A vaginal swab will be collected for wet mount and examined microscopically for presence of lactobacillus. The fCO₂ laser treatment will be performed, and patient will score discomfort using the VAS. The provider will score the difficulty of administering the treatment using the VAS. The patient will complete a three-day voiding diary within 1 week prior to Visit 4, which will be collected at Visit 4.

In the event that scheduling difficulties result in treatment visits out of window, the treatment visits will take place no less than 4 weeks apart.

Phone Call (4 weeks +/- 1 week after Visit 3)

Research staff will contact the patient by phone to assess for AEs and administer the PGI-I for overall urogenital symptoms and Perception of Monetary Value.

Visit 4 - 6 Month Follow up (3 months +/- 2 weeks after Visit 3)

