Current medications and AEs will be assessed. Urine dipstick, and urine culture will be performed, if indicated. UTI symptoms will be assessed. The patient will complete a PGI-I for symptom improvement, VSQ, I-QOL, QUID, OAB-q SF, FSFI, GAD-7 and PHQ-8. A vaginal exam, including a cough stress test and VHIS, will be performed. A vaginal swab will be collected for wet mount and examined microscopically for presence of lactobacillus.

Visit 5 – 9 Month Follow up (3 months +/- 2 weeks after Visit 4)

Current medications and AEs will be assessed. Urine dipstick, and urine culture will be performed, if indicated. UTI symptoms will be assessed. The patient will complete a PGI-I for symptom improvement, VSQ, I-QOL, QUID, OAB-q SF, FSFI, GAD-7 and PHQ-8. The patient will complete a three-day voiding diary within 1 week prior to Visit 6, which will be collected at Visit 6.

Visit 6 – 1 Year Follow up (3 months +/- 2 weeks after Visit 5)

Current medications and AEs will be assessed. Urine dipstick, and urine culture will be performed, if indicated. UTI symptoms will be assessed. Urine pregnancy test will be done in women of childbearing capability. The patient will complete a PGI-I for symptom improvement, VSQ, I-QOL, QUID, OAB-q SF, FSFI, GAD-7, PHQ-8, and Perception of Monetary Value. A vaginal exam, including a cough stress test and VHIS, will be performed. A vaginal swab will be collected for wet mount and examined microscopically for presence of lactobacillus. If the patient feels her symptoms have returned and she requests a repeat treatment this will be discussed with the investigator. If the investigator determines, in his/her clinical judgment, a treatment is appropriate the fCO₂ laser treatment will be performed. The patient will score discomfort using the VAS. The provider will score the difficulty of administering the treatment using the VAS.

Visit 7 – 18 Month Follow up(6 months +/- 2 weeks after Visit 6)

Current medications and AEs will be assessed. Urine dipstick, and urine culture will be performed, if indicated. UTI symptoms will be assessed. The patient will complete a PGI-I for symptom improvement, VSQ, I-QOL, QUID, OAB-q SF, FSFI, GAD-7 and PHQ-8. The patient will complete a three-day voiding diary within 1 week prior to Visit 8, which will be collected at Visit 8.

Visit 8 – 2 Year Follow up (6 months +/- 2 weeks after Visit 7)

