Current medications and AEs will be assessed. Urine dipstick, and urine culture will be performed, if indicated. UTI symptoms will be assessed. Urine pregnancy test will be done in women of childbearing capability. The patient will complete a PGI-I for symptom improvement, VSQ, I-QOL, QUID, OAB-q SF, FSFI, GAD-7 and PHQ-8. A vaginal exam, including a cough stress test and VHIS, will be performed. A vaginal swab will be collected for wet mount and examined microscopically for presence of lactobacillus. If the patient feels her symptoms have returned and she requests a repeat treatment this will be discussed with the investigator. If the investigator determines, in his/her clinical judgment, a treatment is appropriate the fCO₂ laser treatment will be performed. The patient will score discomfort using the VAS. The provider will score the difficulty of administering the treatment using the VAS.

Visit 9 – 30 Month Follow up (6 months +/- 2 weeks after Visit 8)

Current medications and AEs will be assessed. Urine dipstick, and urine culture will be performed, if indicated. UTI symptoms will be assessed. The patient will complete a PGI-I for symptom improvement, VSQ, I-QOL, QUID, OAB-q SF, FSFI, GAD-7 and PHQ-8. The patient will complete a three-day voiding diary within 1 week prior to Visit 10, which will be collected at Visit 10.

Visit 10 – 3 Year Follow up (6 months +/- 2 weeks after Visit 9)

Current medications and AEs will be assessed. Urine dipstick, and urine culture will be performed, if indicated. UTI symptoms will be assessed. Urine pregnancy test will be done in women of childbearing capability. The patient will complete a PGI-I for symptom improvement, VSQ, I-QOL, QUID, OAB-q SF, FSFI, GAD-7 and PHQ-8. A vaginal exam, including a cough stress test and VHIS, will be performed. A vaginal swab will be collected for wet mount and examined microscopically for presence of lactobacillus. If the patient feels her symptoms have returned and she requests a repeat treatment this will be discussed with the investigator. If the investigator determines, in his/her clinical judgment, a treatment is appropriate the fCO₂ laser treatment will be performed. The patient will score discomfort using the VAS. The provider will score the difficulty of administering the treatment using the VAS.

VAS. If a treatment is given, the participant will be instructed to follow up with the practitioner per standard of care. Visit 10 will be the final visit.

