Providers will record the difficulty of performing the treatment on a Visual Analog Scale from 0 (not at all difficult) to 10 (most difficult imaginable).

3-Day Voiding Diary

Patients will record each void and urine leak over a 3 day period. Patients will determine if each leak is a stress leak or an urge leak. They will score the level of urgency they experience with each void, based on the Indevus Urgency Severity Scale (IUSS).

Vulvovaginal Symptom Questionnaire (VSQ)

The VSQ was developed to determine the symptoms, emotions, life impact, and sexual impact of vulvovaginal symptoms on postmenopausal women. The questionnaire is comprised of twenty-one questions with "yes" or "no" responses.

SECTION III: POSSIBLE RISKS AND BENEFITS

Ethical Principles

This project will be approved by William Beaumont Hospital's Institutional Review Board (IRB). Adult patients will provide informed consent prior to any study activity. This study will be conducted pursuant to the Declaration of Helsinki: Recommendation Guiding the Medical Doctors in Biochemical Research Involving Human Subjects. Investigators will follow this clinical investigation plan at all times and follow requirements set by Federal Law and Institutional Review Board regulations at all times.

Risks of Study Procedures

Fractional Carbon Dioxide Laser Treatment

Risks of fractional carbon dioxide laser treatment to the vagina are minimal with no previous adverse events reported. Theoretically, risks may include vaginal irritation, bleeding, infection, and damage to surrounding tissue or structures. There also may be a burning sensation and itching, both mild in nature and resolving within 1-2 days.

Risk of Breach of Privacy and Confidentiality

There is a rare risk of breach of privacy and data confidentiality (release of information which personally identifies the patient). Confidentiality procedures will be strictly adhered to when transferring, managing, and analyzing study data. The patient will be assigned a unique study identification number and research information will be stored in a locked, secure cabinet in the Urology Research suite with access limited to authorized research personnel. Study data will be maintained in a password protected file on a shared network that can only be accessed by Urology research personnel.

Benefits

Patients may experience an improvement in urogenital symptoms. They will receive close clinical follow-up and monitoring throughout the study period.

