SECTION IV: DATA SAFETY MONITORING PLAN

Safety Monitoring

Since the risks associated with this observational study are minimal and not outside the scope of routine care for adults with urological symptoms, oversight of data and safety will be primarily the responsibility of the PI and IRB in accordance with federal regulations. Adverse events and concomitant medications will be queried at each patient visit and reported to the PI in real time.

Data Management

Identifiers: Each enrolled patient will be assigned a unique study identification number (SIN). Protected Health Information (PHI) such as name, date of birth, or medical record number will not be used as the SIN. The SIN will consist of three digits, which will be assigned sequentially beginning with 001. A study enrollment log will be maintained and updated by study staff as patients are enrolled in the study. The enrollment log may contain the SIN and patient name, as well as additional identifiers.

Confidentiality: The enrollment log will be stored in a secure locked file cabinet and/or electronically on a drive with restricted access to Urology Research staff only. PHI that may be collected include patient name, address, telephone numbers, email address, medical record number and dates. The patient's birthdate, admission, discharge and procedures dates may also be collected. Only PHI essential to the research study will be utilized. All data collected during the course of the study will be stored in a secure, locked cabinet in the Urology Research

suite. To maintain confidentiality, only personnel directly involved in the research and the individuals and/or organization listed in the Consent Form and Authorization for Disclosure of Protected Health Information (also known as the Informed Consent Form) may have access to the research records. Medical and billing records collected for the purposes of the study will remain confidential, but may be disclosed (released) or used by the following representatives, specified in the Informed Consent Form:

- The investigators (study doctor/clinician, research staff)
- Beaumont Health System
- The patient's health insurance company and/or group health plans and their intermediaries (companies contracted to process claims)

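### Adverse events after repeat lasers are asked about far later than after initial lasers, and not at all once a woman leaves Visit 10

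*Combined protocol and SAP*

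**What the plan says.** All references are to the combined protocol and SAP.

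- **Initial course.** Section II (Methodology) plans three lasers: treatments with the "laser to the vagina will be performed, approximately six weeks apart". Study Visits gives the windows. The second is "Visit 2 – Treatment 2 (6 weeks +/- 2 weeks after Visit 1", and Visit 3 follows Visit 2 on the same terms. AEs are assessed at both. A phone call is due 4 weeks +/- 1 week after Visit 3: "Research staff will contact the patient by phone to assess for AEs".
- **Repeat lasers.** Section II states: "The patient will be offered a repeat treatment at 1, 2 and 3 years if initial treatment efficacy has decreased". The visit texts place these at Visits 6, 8 and 10, on returned symptoms, the woman's request and the investigator's agreement.
- **Contact after a repeat laser.** Visit 7 is the "18 Month Follow up(6 months +/- 2 weeks after Visit 6"; Visit 9 has the same interval after Visit 8. Both include an AE assessment. After a Visit 10 laser the "participant will be instructed to follow up with the practitioner per standard of care. Visit 10 will be the final visit".
- **General rule.** Section IV (Safety Monitoring) says: "Adverse events and concomitant medications will be queried at each patient visit and reported to the PI in real time".
- **Same-day assessment.** Visit 1 has AEs assessed throughout the visit. At Visits 6, 8 and 10 the AE assessment opens the visit text, the laser comes later, and no timing relative to the laser is given. The discomfort VAS is scored for each laser.
- **Expected effects.** Section III (Risks of Study Procedures) describes burning and itching, "both mild in nature and resolving within 1-2 days", and lists irritation, bleeding, infection and tissue damage as theoretical risks.

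**The concern.** The same procedure is followed up in two different ways. In the initial course a woman is asked about AEs within weeks. When the laser is repeated she is asked about half a year later or, after Visit 10, not again. Effects lasting a day or two are the ones most easily lost to six-month recall. An infection or bleed that starts after she leaves Visit 10 has no scheduled route into the study data.

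This matters because the plan intends to use the AE data. Section IV has the monitor review events by visit number and severity, and Section V proposes to explore possible complications. With uneven ascertainment, repeat lasers would tend to show fewer short-lived effects than initial ones even if the true rates were equal. A reader of the results could not tell a lower rate from weaker follow-up.

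**Working it through.** The plan gives no figure to reproduce here. The check measures the time from each laser to the next scheduled AE query, then counts the lasers affected. The windows come from the visit descriptions; the Schedule of Activities table could not be read reliably in the text available and was not used.

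**Step 1: time to the next AE query, visits in window**

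Six months in weeks: 6 x 365.25 / (12 x 7) = 26.1. With +/- 2 weeks: 24.1 to 28.1.

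| Laser | Next scheduled AE query | Gap |
|---|---|---|
| Visit 1 | Visit 2, 6 +/- 2 weeks | 4-8 weeks |
| Visit 2 | Visit 3, 6 +/- 2 weeks | 4-8 weeks |
| Visit 3 | Phone call, 4 +/- 1 weeks | 3-5 weeks |
| Visit 6 (repeat) | Visit 7, 6 months +/- 2 weeks | about 24-28 weeks |
| Visit 8 (repeat) | Visit 9, 6 months +/- 2 weeks | about 24-28 weeks |
| Visit 10 (repeat) | None after the visit | none scheduled |

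Against the 4-week call the repeat gap is 26.09 / 4 = 6.5 times as long; against the 6-week interval it is 26.09 / 6 = 4.3 times.

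**Step 2: whether another provision closes the gap**

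- The phone or mail option under Study Visits is for women who cannot attend Visits 4 to 10. It replaces a visit and is not an extra call after a laser.
- Section IV ties AE queries to visits.
- The fixed monitoring points in Section IV run up to 80 completed 16-week calls and then move to the end of the study. Anything between is as needed.

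None of these schedules a query after a repeat laser.

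**Step 3: share of possible lasers per woman**

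Initial 3 + repeat up to 3 = 6. Repeats are at most 3/6 = 50%: 2/6 with a gap of about six months and 1/6 with no later query.

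**Step 4: number of lasers**

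Section II gives about 100 women. Uptake u at each repeat visit is not stated, so a range is assumed, with all 100 women retained for three years.

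- Repeat lasers = 300u
- All lasers = 300 + 300u
- Lasers at Visit 10 = 100u

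| u (assumed) | Repeat lasers | Share of all lasers | At Visits 6 and 8 | At Visit 10 |
|---|---|---|---|---|
| 20% | 60 | 60/360 = 17% | 40 | 20 (20/360 = 6%) |
| 60% | 180 | 180/480 = 38% | 120 | 60 (60/480 = 13%) |
| 100% (ceiling) | 300 | 300/600 = 50% | 200 | 100 (100/600 = 17%) |

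**Step 5: effect of the fix**

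A call at 4 +/- 1 weeks after each repeat laser cuts the gap at Visits 6 and 8 from about 26 weeks to 3-5 weeks. At Visit 10 it replaces no later query with one at 3-5 weeks.

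**The case against.** The best defence is that AE collection for repeat lasers is late rather than absent, that repeats are optional, and that the plan treats the risk as minimal and names no safety outcome. Much of this stands, and it rules out several stronger readings.

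- **That nobody asks about AEs after repeat lasers.** A reader might infer this, but Visits 7 and 9 both include an AE assessment. Events that led to care, a medication change or lasting symptoms could still surface there. The likely loss is of mild, short-lived effects.
- **That Visit 10 lasers yield no AE data.** The documents do not support this. AEs are assessed on the day and discomfort during the laser is scored. Section IV also names the medical record as a data source and provides for chart review. What is missing is a scheduled query after the visit; nothing says the passive routes would reach care given after Visit 10.
- **That the gap contradicts the real-time reporting sentence in Section IV.** It does not. That sentence ties the query to visits; the real-time part describes passing on what is found.
- **That half of all lasers are affected.** Half is the ceiling, reached only if every woman takes all three optional repeats.
- **That every laser needs a daily symptom record.** This goes beyond the defect, since the initial course already has contact at 3-8 weeks and the one-to-two-day duration is risk wording, not a study hypothesis.

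The consent pages are also not in the text available, so an instruction there to report problems between visits cannot be excluded. Such an instruction would still be passive reporting and would not match the active query after the initial lasers.

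**Conclusion.** The concern holds as a difference in ascertainment. An AE query is scheduled 3-8 weeks after an initial laser, about 24-28 weeks after a Visit 6 or 8 laser, and never after a woman treated at Visit 10 has left. Whether same-day assessment at Visits 6, 8 and 10 covers the period after the laser is unstated. The intervals come straight from the protocol's windows and need no assumption. The volume (60-180 repeat lasers, 17-38% of all lasers, 20-60 at Visit 10) rests on assumed uptake of 20-60% at each repeat visit and full retention of 100 women; the gap exists at any uptake above zero.

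The primary endpoint at week 16 precedes any repeat laser and is unaffected. This should be changed because it bears on the safety record and is cheap to correct; it does not undermine the main analysis.

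**What to change.** 1. Extend the AE phone call already used after Visit 3 (4 +/- 1 weeks) to every repeat laser at Visits 6, 8 and 10. Keep the AE record open until that call, and reword the Visit 10 text so that the call is part of the study.
2. State that on laser days AEs are also assessed after the laser.
3. In Section V, report AEs per laser, for initial and repeat lasers separately, with the number of lasers that had a post-laser contact as the denominator that readers can check.

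This changes data collection and reporting only; it leaves the treatment and the retreatment decision as they are. The cost is one short call per repeat laser by existing staff (60-180 calls under the uptake assumed above, 300 at most) and closure about 3-5 weeks later for women treated at Visit 10.

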Laser treatment will be performed as per routine protocol. This includes intra-vaginal treatment based on atrophy level as based on VHIS score and treatment number.

Treatment	Atrophy	Treatment 1	Treatment 2	Treatment 3
Intravaginal	Severe (VHIS 6-15)	Energy: 7.5-10 mJ Density: 10%	Energy: 10 mJ Density: 10%	Energy: 10 mJ Density: 10%
	Moderate (VHIS 16-20)	Energy: 10 mJ Density: 10%	Energy: 10-12.5 mJ Density: 10-15%	Energy: 10-12.5 mJ Density: 10-15%
	Non-atrophic (VHIS >20)	Energy: 10 mJ Density: 10%	Energy: 12.5 mJ Density: 10-15%	Energy: 12.5 mJ Density: 15%

Laser is delivered at 6 points at each level of the vaginal wall: 12, 2, 4, 6, 8, and 10, o'clock of Hart's line. Delivery begins at the most proximal and the wand is retracted by 1 cm and another row of laser treatment is delivered. Number of levels is determined by patient vaginal length.

MEASURES

Cough Stress Test

During a vaginal exam, while the patient is in lithotomy or frog-legged position, the provider will ask the patient to cough and will look for visual signs of a urine leak. Any urine loss observed is indicative of a positive cough stress test.

Female Sexual Function Index (FSFI)

This validated questionnaire is a brief multidimensional scale for assessing sexual function in women. The scale has received initial psychometric evaluation, including studies of reliability, convergent validity, and discriminant validity²⁴.

Generalized Anxiety Disorder 7-item (GAD-7)

This validated questionnaire is used for screening for anxiety with good reliability with sensitivity of 89% and specificity of 82%, for use in clinical practice and in research²⁵.

Incontinence-Quality of Life (I-QOL)

This validated questionnaire is a commonly used self-report quality of life measure specific to urinary incontinence. This tool can be used to assess the impact of urinary problems and their treatment. The I-QOL has 22 questions with the following 3 subscales: avoid and limiting behaviors (items), psychosocial impacts (9 items), and social embarrassment (5 items). It is easily self-administered and takes about 5 minutes to complete.²³

Overactive Bladder Questionnaire-Short Form (OAB-q SF)

This validated measure evaluates overactive bladder symptom severity and health related quality of life (Coyne, 2015). Statistically significant correlations have been found between the OAB-q SF scales and other patient reported outcomes instruments. For example, higher levels of depressive symptoms as measured by the Center for Epidemiologic Studies Depression Scale (CES-D) were linearly related to higher levels of Symptom Bother (r 0.31, P<0.0001) and lower levels of health related quality of life (HRQL) on the OAB-q SF (r 0.35, P<0.0001). Both the Symptom Bother and HRQL scales easily differentiated between controls without overactive bladder (OAB), continent patients with OAB and incontinent OAB patients (P<0.0001).

Patient Global Impression of Improvement (PGI-I)

The Patient Global Impression of Improvement (PGI-I) will be used to evaluate the patients' perceptions of overall improvement after treatment. The questionnaire has been validated in several urogenital conditions²¹⁻²³.

Personal Health Questionnaire Depression score (PHQ-8)

This validated questionnaire is used for monitoring depression severity and response to treatment and can be used to screen for depression in at-risk populations.

Perception of Monetary Value

The laser treatments will be provided at no cost to the study participants. This questionnaire will be completed at the primary endpoint (16 weeks) and the 12 month visit.

Questionnaire for Urinary Incontinence Diagnosis (QUID)

This validated measure is used to evaluate improvement in stress-predominant urinary incontinence in women undergoing non-surgical treatment. It has been found to be valid and responsive with internal consistency and acceptable psychometrics characteristics for use in clinical trials²⁴.

Vaginal Health Index Score (VHIS)

The VHIS is a tool, used by providers, to determine if vaginal atrophy is present. Providers perform a vaginal exam and give a score of 1-5 (abnormal to normal, respectively) on each of the following vaginal parameters: elasticity, secretion/fluid volume, vaginal pH, integrity of the epithelium, and lubrication/moisture of the vaginal wall. A VHIS score less than 15 is indicative of vaginal atrophy.

Visual Analog Scale (VAS) for Pain/Discomfort

Patients will record their average pain score during treatment from 0 (no pain) to 10 (most severe pain imaginable) on a Visual Analog Scale for pelvic pain and discomfort.

Visual Analog Scale (VAS) for Procedure Difficulty

Providers will record the difficulty of performing the treatment on a Visual Analog Scale from 0 (not at all difficult) to 10 (most difficult imaginable).

3-Day Voiding Diary

Patients will record each void and urine leak over a 3 day period. Patients will determine if each leak is a stress leak or an urge leak. They will score the level of urgency they experience with each void, based on the Indevus Urgency Severity Scale (IUSS).

Vulvovaginal Symptom Questionnaire (VSQ)

The VSQ was developed to determine the symptoms, emotions, life impact, and sexual impact of vulvovaginal symptoms on postmenopausal women. The questionnaire is comprised of twenty-one questions with "yes" or "no" responses.

SECTION III: POSSIBLE RISKS AND BENEFITS

Ethical Principles

This project will be approved by William Beaumont Hospital's Institutional Review Board (IRB). Adult patients will provide informed consent prior to any study activity. This study will be conducted pursuant to the Declaration of Helsinki: Recommendation Guiding the Medical Doctors in Biochemical Research Involving Human Subjects. Investigators will follow this clinical investigation plan at all times and follow requirements set by Federal Law and Institutional Review Board regulations at all times.

Risks of Study Procedures

Fractional Carbon Dioxide Laser Treatment

Risks of fractional carbon dioxide laser treatment to the vagina are minimal with no previous adverse events reported. Theoretically, risks may include vaginal irritation, bleeding, infection, and damage to surrounding tissue or structures. There also may be a burning sensation and itching, both mild in nature and resolving within 1-2 days.

Risk of Breach of Privacy and Confidentiality

There is a rare risk of breach of privacy and data confidentiality (release of information which personally identifies the patient). Confidentiality procedures will be strictly adhered to when transferring, managing, and analyzing study data. The patient will be assigned a unique study identification number and research information will be stored in a locked, secure cabinet in the Urology Research suite with access limited to authorized research personnel. Study data will be maintained in a password protected file on a shared network that can only be accessed by Urology research personnel.

Benefits

Patients may experience an improvement in urogenital symptoms. They will receive close clinical follow-up and monitoring throughout the study period.

SECTION IV: DATA SAFETY MONITORING PLAN

Safety Monitoring

Since the risks associated with this observational study are minimal and not outside the scope of routine care for adults with urological symptoms, oversight of data and safety will be primarily the responsibility of the PI and IRB in accordance with federal regulations. Adverse events and concomitant medications will be queried at each patient visit and reported to the PI in real time.

Data Management

Identifiers: Each enrolled patient will be assigned a unique study identification number (SIN). Protected Health Information (PHI) such as name, date of birth, or medical record number will not be used as the SIN. The SIN will consist of three digits, which will be assigned sequentially beginning with 001. A study enrollment log will be maintained and updated by study staff as patients are enrolled in the study. The enrollment log may contain the SIN and patient name, as well as additional identifiers.

Confidentiality: The enrollment log will be stored in a secure locked file cabinet and/or electronically on a drive with restricted access to Urology Research staff only. PHI that may be collected include patient name, address, telephone numbers, email address, medical record number and dates. The patient's birthdate, admission, discharge and procedures dates may also be collected. Only PHI essential to the research study will be utilized. All data collected during the course of the study will be stored in a secure, locked cabinet in the Urology Research

suite. To maintain confidentiality, only personnel directly involved in the research and the individuals and/or organization listed in the Consent Form and Authorization for Disclosure of Protected Health Information (also known as the Informed Consent Form) may have access to the research records. Medical and billing records collected for the purposes of the study will remain confidential, but may be disclosed (released) or used by the following representatives, specified in the Informed Consent Form:

- The investigators (study doctor/clinician, research staff)
- Beaumont Health System
- The patient's health insurance company and/or group health plans and their intermediaries (companies contracted to process claims)

If the patient requests information be shared with additional parties not listed on the Informed Consent (i.e. a primary care physician), a fully completed and signed Authorization for Disclosure of Subject Medical Information will be required prior to the release of study data.

Study data will be entered into a password protected database maintained on a local network within the Department of Urology. Access to the local network is restricted to Urology personnel, and access to the study database will be restricted to the study's key personnel only. Data will be entered by patient study identification number; names will not be linked with patient data in the database.

Our research practices safeguard the identity of study patients throughout the course of the study, including the dissemination of study findings. Study patients are not identified in any publication or other release of study results, data, and other information (such as professional writings, at professional meetings, in the sponsor's product information, and/or advertising or other promotional materials).

To assure patient privacy during the informed consent process, discussions may be conducted in a designated consenting room within the WUC or Urology Research Clinical suite. The rooms are separated from the reception, exam, lab, and office areas, and the doors are closed during discussions with research patients.

Data capture, verification, and disposition: Data may be captured from a number of sources including patient report, the electronic medical record, patient-administered questionnaires, clinical assessments, and diagnostic evaluations. All data entered on the case report form (CRF) is substantiated and verified by appropriate source documentation. Study data will be transcribed by study personnel from the source documents onto the CRF. Data recorded on the CRF will be entered into the database.

Clinical Monitoring Plan: Urology research nurse clinician(s) not participating in patient recruitment, enrollment, study visits or other study activities will be assigned to review completed case report forms and/or electronic data entry, data base review, IRB decisions, and investigator and clinical site records throughout the study. Additionally, patient charts, and clinical records will be reviewed to assure protocol adherence. Source documentation may also be verified.

He/she will review and verify the accuracy of data collection and documentation at the following time points:

- After the first patient has completed Visit 3
- After the first 6 patients have completed Visit 3
- After 20 patients have completed the 16-week phone call visit
- After 40 patients have completed the 16-week phone visit
- After 60 patients have completed the 16-week phone visit
- After 80 patients have completed the 16-week phone visit
- At the end of the study
- Additional monitoring may occur as needed

Patient records will be reviewed to verify CRF completion and delinquencies, and capture protocol deviations and frequency of unanticipated problems/adverse events. In order to identify, evaluate, and prevent adverse events, the total number of events will be reviewed, as well as the details of each event, including visit number and severity. Data will be reviewed to identify trends and possible concerns. Enrollment data will direct recruitment efforts and assist in study planning.

The overall objectives of routine monitoring are to:

- Document clinical study progress.
- Document that the protocol and associated forms are current.
- Obtain and review current clinical data, reports, and source documents.
- Review the overall study status including verification of the study files. All required documents and records should be accurate, complete, and current.
- Confirm that all patients have signed the informed consent form.
- Confirm that all enrolled patients have met the eligibility criteria.
- Verify accuracy of transferring data from source document(s) to the case report forms (CRFs) to the database.
- Confirm complete, accurate, and timely event reporting.
- Confirm adequacy of staff and facilities.
- Review communication records.
- Verify identification and reporting of protocol violations.

Outcomes of all scheduled and unscheduled study monitoring will be documented. Follow-up action items will be included in the report. The monitoring summary report will be forwarded to the PI and research coordinator.

Quality Control and Quality Assurance

The PI or designee has primary responsibility for QC/QA activities of the data. Beaumont's Research Institute also audits investigator-initiated studies to ensure compliance with consent processes and reporting requirements. The key QC/QA activities for the study will be:

- Clearly formatted and carefully constructed Case Report Forms (CRF);
- Sign-Off Procedures for all CRFs;
- Verification of patient eligibility at each visit

A database will be created utilizing RedCap, MS Excel, or equivalent software. Only designated study personnel will have access to the database, which will be stored on the Urology Research Department's shared drive. Access to the computerized system will be password protected. To ensure accuracy of data entry, database entries will be cross-checked against source

documents. The shared drive is backed up nightly to ensure minimal data loss, even in the most catastrophic system failure. The database will be active until all study visits are completed, final monitoring activities have been conducted, and all data queries have been resolved. After that time, the database will be locked, prohibiting any changes to the data.

All study records, including both paper and electronic, will be stored in accordance with all federal and institutional requirements, including, but not limited to, the HIPAA Privacy Rule, the Food and Drug Act, and Medicare policy. The stored data will be kept in a secure, protected manner. All records will be retained, at a minimum, for eleven years beyond study completion.

SECTION V: STATISTICAL CONSIDERATIONS AND DATA ANALYSIS

This is a novel observational study without a comparison group. Therefore, a power calculation is not necessary. Descriptive statistics will be given for all data collected. Patients will be analyzed and described overall as a group, and subgroup analyses will be performed by presenting complaint(s). Missing data will be considered missing and no interpolations or substitutions will be performed. Categorical characteristics will be summarized using frequencies and percentages. Continuous characteristics will be summarized using mean and standard deviation for normally distributed variables and median and 25th and 75th percentiles for those not normally distributed. The changes in the continuous measures from baseline (prior to device implant) to Visit 4 may be examined using paired t tests. We will explore relationships within this group of patients with possible complications using appropriate methods. SAS for Windows version 9.3 Cary, NC or equivalent will be used for all analyses.

SECTION VI: REFERENCES

1. Nappi RE and Kokot-Kierepa M. Women's voices in the menopause: results from an international survey on vaginal atrophy. *Maturitas*. 2010; 67: 233-8.
2. Nappi RE and Palacios S. Impact of vulvovaginal atrophy on sexual health and quality of life at postmenopause. *Climacteric*. 2014; 17: 3-9.
